## 14.2 PROTOCOL DEVIATIONS, BREACHES AND WAIVERS

The CI will not implement any deviation from the protocol without agreement from the Sponsor, except where necessary to eliminate an immediate hazard to study participants.

In the event that the CI/PI needs to deviate from the protocol, the nature of and reasons for the deviation will be recorded in the CRF, documented in the study Deviation Log and notified to the Sponsor. If this necessitates a subsequent protocol amendment, this will be submitted to the Sponsor for approval and then to the appropriate REC and local NHS R&D for review and approvals as appropriate. It is Sponsor policy that waivers to the Protocol will not be approved.

In the event that a serious breach of the protocol or GCP is suspected, this will be reported to the Sponsor immediately using the form Notification to Sponsor of Potential Serious Breach of Good Clinical Practice (GCP) or Study Protocol.

## 14.3 STUDY RECORD RETENTION

Archiving of study documents and electronic data will be carried out as per SOPs of the Sponsor. All study documentation and electronic data will be kept for at least 15 years. TCTU will provide the TMF and electronic study data, via Sponsor approved (and funded) courier transfer; this will be stored on behalf of the CI within the Data Safe Haven (DASH), University of Aberdeen. ISFs and CRFs will be archived locally at sites, the Archive Approval Form (TMP QA 34) will be completed by sites and provided to the Study Coordinator / delegate for inclusion with the TMF archive. At the end of the archiving period destruction will be carried out as per Sponsor SOP.

## 14.4 END OF STUDY

The end of study is defined as database lock. The Sponsor or CI have the right at any time to terminate the study for clinical or administrative reasons.

The end of the study will be reported to the Sponsor, REC, and NHS R&D Office(s) within 90 days, or 15 days if the study is terminated prematurely. The CI will ensure that any appropriate follow up is arranged for all participants.

A final report of the study will be provided to the Sponsor and REC within 1 year of the end of the study.

Main study results will be posted to a publicly-available Clinical Trials Registry (ISRCTN) within 1 year of the end of the study.

## 14.5 CONTINUATION OF TREATMENT STRATEGY FOLLOWING THE END OF THE STUDY

The participants will be able to make informed decision (based on their study experience) and discuss with their GPs for their preferred treatment option. This empowers patients to use autonomy and promote shared-decision making.

## 15 REPORTING, PUBLICATIONS AND NOTIFICATION OF RESULTS

## 15.1 AUTHORSHIP POLICY

Ownership of the data arising from this study resides with the study team and their respective employers. On completion of the study, the study data will be analysed and tabulated, and a clinical study report will be prepared.

## 15.2 PUBLICATION

The clinical study report will be used for publication and presentation at scientific meetings. Study investigators have the right to publish orally or in writing the results of the study. Summaries of results will also be made available to Investigators for dissemination within their clinical areas (where appropriate and according to their discretion).

## 15.3 PEER REVIEW

The grant proposal for this study has been subjected to external peer review via the Chief Scientist Office, Scottish Government - the funding body.

## 15.4 DATA SHARING

At the end of the study, study data will be archived; pseudo-anonymised study data will be made available on request to other bona fide academic investigators via data sharing agreements overseen by the University of Aberdeen.

#### 15.5 DISSEMINATION PLAN

Results will be disseminated through public engagement activities led by the study team with support from the Public Engagement in Research Unit (PERU) of the University of Aberdeen with input from our lay service users. In particular we will be taking advantage of the internationally-excellent programme which Aberdeen has in engaging with members of the public in research: http://www.abdn.ac.uk/engage. Our dissemination activities will also benefit from the Service Users' Groups, locally established networks of volunteer members of the public who actively wish to contribute in research by working alongside the researchers in delivering successful research studies and disseminating to wide ranging beneficiaries including patients, public, health care providers, commissioners and policy makers. We also have extensive Cafe series in University of Aberdeen-*CafeMed*, http://www.abdn.ac.uk/news/9087, *Cafe Scientifique* and *May Festival* - as public engagement mechanisms and such programmes provide excellent opportunities to the researchers for public engagement.

Through our respective communication departments, we will advertise the study widely to the public through press and media from funding stage to dissemination of results. At the end of the study, we will invite participants and family members to attend a tea party (at each site) to share the results with them and receive their formal (written feedback on a feedback form) and informal feedback (through conversation with the research team members) on how the study went, and ways to improve future study design.

## **APPENDIX 1: PARTICIPANT REPORTED SYMPTOMS**

Participant I	D:		Date:							
			D	D	-	Μ	Μ	-	Υ	Υ

#### **Baseline Participant Reported Symptoms**

Over the last week, how much have the following symptoms affected you?

Symptom	Not at all	A little	Somewhat	Quite a lot	A great deal
Feeling tired					
Being out of breath when I walk					
Being out of breath when I am at rest					
Feeling dizzy or lightheaded					
Having a sore tongue					
Having restless legs during sleep					
Having cramps in my legs at night					

Version 1

10/01/18

## **APPENDIX 2: ORAL IRON USE SCALE**

Baseline Oral Iron Use (Self-report)

#### Please read each statement then tick or circle one response

Since starting oral iron (tablets or medicine)

1.	I have forgotten to take it						
	Very Often	Often	Sometimes	Rarely	Never		

I take it at the same time every day

						
	Always	Usually	Sometimes	Rarely	Never	

- 3. When I feel better I stop taking it

   Always
   Usually
   Sometimes
   Rarely
   Never
- 4. When I feel worse I stop taking it

   Always
   Usually
   Sometimes
   Rarely
   Never

Version 1

14/06/18

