#### 2.2.2 Secondary Outcomes

- 1) Change in haemoglobin levels between baseline and 3 months
- 2) Change in ferritin levels between baseline and 3 months
- 3) Number of eligible patients per site
- 4) Proportion of eligible patients agreeing to take part and passing screening
- 5) Feasibility of collecting proposed outcomes at baseline and 3 months for a future definitive trial:
  - Short physical performance battery (15)
  - Six-minute walk distance
  - Anaemia-related symptoms (e.g. breathlessness, tiredness, fatigue)
  - Health-related quality of life (EQ-5D-5L™, 15D©) (16, 17) (20)

- Activities of daily living (NEADL©) (18)
- Health care use including use of blood transfusions and hospitalisation
- All-cause mortality
- 6) Dropout rate at 3 months
- 7) Crossover rate at 3 months
- Change in functional limitation (six-minute walk <400m or short physical performance battery score ≤10) scores between baseline and 3 months
- Change in level of fatigue assessed using validated Fatigue Severity Scale (19) between baseline and 3 months
- 10) Change in medication adherence using Oral Iron Use Likert scale (in those taking oral iron only) between baseline and 3 months
- 11) Participant experience using semi-qualitative questionnaire at 3 months.

[figure not shown]

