#### 4.2 INCLUSION CRITERIA

To be eligible, the participant will be assessed, and must meet all of the following criteria:

- 1. Provision of written informed consent
- 2. Community dwelling (i.e. not in hospital)
- 3. Age 65 years or over
- 4. Haemoglobin of >=85g/L and <=110g/L prior to commencing oral iron
- 5. Ferritin <100µg/L prior to commencing oral iron
- 6. Currently taking oral iron at any dose with a minimum of 8 weeks therapy
- Insufficient response to oral iron therapy (sufficient response defined as improvement in Hb of 20g/L after a minimum of 8 weeks of oral iron therapy or above lower limit of normal Hb level for sex)
- 8. Relevant investigations (including upper and lower GI endoscopies) either already conducted, offered but declined by the patient, or deemed not appropriate by the treating clinician. Only if applicable:
- 9. Oral iron therapy provided an initial sufficient response however Hb has now fallen below lower limit of normal for sex (Sufficient response is defined as an improvement in Hb of 20g/L or Hb above lower limit of normal for sex after a minimum of 8 weeks of oral iron therapy).

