#### 7.1.4 Follow-up Outcome Assessment Visit

See study matrix (Table 4)

The following will be performed by the blinded RN at the outcome assessment visit:

- 5ml of non-fasted blood will be taken for local laboratory haematological and biochemical analysis:
  - Haemoglobin and Ferritin
- Assessment of Physical function:
  - Timed up and Go Test (TUG).
  - Short Physical Performance Battery (SPPB)(15).
  - o Six-minute Walk Test.

Details of the procedures and equipment used for these tests of physical function will be provided in the study Operations Manual.

- Health and social activity will be collected using the following self-reported questionnaire data collection tools (non-validated tools are provided as appendices):
  - Fatigue Severity Score (19)
  - o Patient Reported Anaemia Symptoms
  - EQ5D5L (quality of life) (16, 17)
  - o 15D (health related quality of life) (20)
  - NEADL score (activities of daily living) (18)
  - o Health & Care Use
  - Participant experience and views (Appendix 4)

For participants randomised to receive oral iron the unblinded RN will telephone the participant to complete the Oral Iron Use Likert Scale.

After study assessments have been carried out, and to preserve blinding, the following will be collected from participants and their medical notes:

- Adverse events
- Medication review.

Participants will be provided with iron specific dietary advice (24) at the end of the Follow-up visit.

At the end of study participation the GP will resume care and iron prescribing; additionally:

- the RN will direct the participant to contact their GP
- the GP will be directed (via GP letter recruited) to review Visit 4 Hb and ferritin results.

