#### 8 DATA COLLECTION & MANAGEMENT

#### 8.1 DATA COLLECTION

It is the CI's responsibility to ensure the accuracy of all data entered and recorded in the CRFs, the database and spreadsheets. The Delegation of Responsibilities Log will identify all study personnel responsible for data collection, entry and discrepancy management.

The paper CRF, designed by TCTU and approved by the CI, Statistician and Health Economist, will be issued to sites following site activation. Competed CRFs will be stored in a secure, restricted access storage facility.

The data will be collected by the RN, or other delegated person and/or the Site PI and entered into a paper CRF. Information will then be transferred contemporaneously (and within a maximum of 10 working days), by delegated staff, to the web-based study electronic database run in OpenClinica or

the PMS hosted by HIC. Delegated staff will carry out visual verification of data entered from CRF to OC; this quality control activity will be logged and a copy provided to the trial manager / delegate for review. All research data and data established from the NHS tests will be stored in an unidentifiable format on this secure, password protected database hosted by HIC, University of Dundee.

The PMS will be updated by delegated staff; this will provide co-primary outcome recruitment data. Screening activity will be entered onto the Screening Activity Excel spreadsheet; this will be updated and provided each month to the Trial Manager / delegate.

To preserve blinding the follow-up Oral Iron Use Scale (oral iron only), iron treatment and Participant Experience and Views questionnaires will be quarantined. The unblinded RN will transfer the Oral Iron Use Scale and iron treatment data onto version controlled Excel spreadsheets. LabKey will be used to securely upload the Excel Oral Iron Use Scale and iron treatment data files and Participant Experience questionnaires. Following data lock these data will be analysed separately from the main dataset; by the Health Economics Research Unit (HERU) based in the University of Aberdeen.

The medical notes or electronic health records will provide source data for past medical history, prescriptions, subsequent medical conditions, hospital admissions, diagnostic reports and blood results.

NOTE: To preserve blinding, the blinded RN should avoid reviewing the medical record until followup outcome assessments have been completed.

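### The printed Oral Iron Use Scale has an open-ended, patient-specific recall period, which does not fit an outcome defined as change in adherence from baseline to 3 months

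*Protocol*

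**What the plan says.** Protocol Section 2.2.2, item 10, defines the outcome as "Change in medication adherence using Oral Iron Use Likert scale (in those taking oral iron only) between baseline and 3 months".

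Appendix 2 prints one form of the scale. It is headed "Baseline Oral Iron Use (Self-report)", and its four items stand under the stem "Since starting oral iron (tablets or medicine)". No other recall period for this scale appears in the protocol.

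The time on oral iron before entry follows from Section 4.2, which requires participants to be "Currently taking oral iron at any dose with a minimum of 8 weeks therapy". No maximum is set.

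Table 4 schedules the scale at Visit 1 for everyone and at Visit 4 for those randomised to continue oral iron. At baseline it is self-reported (Section 7.1.1). At follow-up, Section 7.1.4 says that "the unblinded RN will telephone the participant to complete the Oral Iron Use Likert Scale". Section 8.1 speaks of a follow-up version: "To preserve blinding the follow-up Oral Iron Use Scale (oral iron only), iron treatment and Participant Experience and Views questionnaires will be quarantined". Section 7.1.4 also says that "non-validated tools are provided as appendices", but only the baseline form of this scale is there.

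**The concern.** A change score is easiest to read when both answers cover periods of the same length, one before the trial treatment period and one inside it. The printed stem starts the clock when oral iron began, so the baseline period is different for each participant. It may be long: Section 1.1 says that many people treated for iron deficiency are on long-term treatment, and criterion 9 in Section 4.2 admits people who first responded to oral iron and later relapsed.

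If the same stem were used at 3 months, the answer would cover the pre-trial period a second time. A participant who took iron reliably for a year and then missed most doses during the trial could still give a fairly adherent-looking answer, and the change would be pulled toward zero. Moving from a self-completed form to a nurse's telephone call adds a second difference between the two measurements that has nothing to do with adherence.

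Adherence in the continue arm bears on how the comparison of continuing with stopping is read, and Section 1.1 itself names poor adherence to oral iron as a problem. The prescription linkage in Section 5.2 is another adherence measure, but it is confined to Fife, with at most 21 participants over all three arms (Section 9.1).

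**Working it through.** The protocol gives no figure that depends on this scale, so there is none to reproduce. The check has two parts.

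**1. Recall periods side by side**

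| Form | Recall period printed |
|---|---|
| Appendix 1, participant-reported symptoms | the last week |
| Appendix 2, Oral Iron Use Scale (baseline form) | from the start of oral iron, no fixed length |
| Appendix 3, Care Use Questionnaire | the past three months |

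The two other appended forms that print a recall period fix its length. Appendix 2 does not.

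**2. Dilution if the stem is reused (illustration)**

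Inputs:
- p = weeks on oral iron before entry. The minimum is 8 (Section 4.2). Larger values are assumptions, since no maximum or distribution is given.
- f = weeks from entry to follow-up. Three months is taken as 13 weeks; the ±3-week window in Table 4 gives 10 to 16.
- Assumptions: the same stem at follow-up, and an answer that reflects average behaviour with equal weight on every week.

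The baseline answer then reflects the pre-trial level A. With an on-trial level B, the follow-up answer reflects (p·A + f·B)/(p + f). The difference is (B − A)·f/(p + f), so the share of the true change that shows is f/(p + f).

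| p (weeks) | f = 13 | f = 10 to 16 |
|---|---|---|
| 8 | 13/21 = 62% | 56% to 67% |
| 26 | 13/39 = 33% | 28% to 38% |
| 52 | 13/65 = 20% | 16% to 24% |
| 104 | 13/117 = 11% | 9% to 13% |

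In months, 3/(T + 3) gives nearly the same: 3/5 = 60% at T = 2, 3/9 = 33% at T = 6, 3/15 = 20% at T = 12 and 3/27 = 11% at T = 24.

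The dilution therefore varies with prior duration. Two participants with the same true change would show different changes on the scale.

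**If the follow-up form uses another stem**, for example one that starts at randomisation, p drops out of the follow-up answer and this dilution disappears. What is left is a baseline answer over 8 weeks or more, possibly years, set against a follow-up answer over about 13 weeks.

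**Would a 4-week period fit?** At baseline everyone has at least 8 weeks of oral iron, so 4 weeks lie wholly within pre-trial use. At follow-up the earliest visit is at about 10 weeks, so 4 weeks lie wholly within the trial period.

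**The case against.** The strongest reply is that the follow-up form is not shown. The printed form is labelled as the baseline one, Section 8.1 names a follow-up scale, and Appendix 1 likewise prints only a baseline version of a tool that is used again later. At baseline, the time since oral iron began is a natural pre-trial reference. If the follow-up form asks about the period since randomisation, the comparison is pre-trial against on-trial behaviour, which is a change in adherence. The response options are frequencies rather than counts, so unequal periods do not by themselves make the scores incomparable. This stands, and it is why the second branch is the lesser problem.

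A reader might infer that the scale cannot measure change at all. The documents do not support that. Reuse of the stem is not stated, and even then the change would be diluted, not abolished. Items 2 to 4 are in the present tense, so respondents may answer them for current behaviour; only item 1, on forgetting, is plainly cumulative. Equal weighting of all past weeks is an assumption, and the scale is four ordinal items, not a share of doses taken.

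A reader might also infer that, outside Fife, nothing else would reveal a continue-arm participant who stopped oral iron. That goes too far. The protocol also has a crossover rate (Section 2.2.2, item 7), a medication review at Visit 4 (Section 7.1.4), separately held iron treatment data (Section 8.1) and the participant's own report of treatment received (Appendix 4, question 4). These would pick up stopping, though none is described as grading missed doses.

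On mode, the telephone call by the unblinded nurse and the quarantine of the data protect the blinded assessor, and the answers remain the participant's own. No bias from the mode change is demonstrated; it is an avoidable difference.

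What the reply does not remove is the printed baseline stem. Whatever the follow-up form says, that stem sets no common length for the baseline period.

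**Conclusion.** The concern holds in a limited form. The one form printed has a recall period that differs by patient, while outcome 10 is a change over a fixed interval. With the stem reused and even averaging over time, about 60% of a true change would show after 2 months of prior use, 33% after 6 months and 20% after 12 months. Those percentages rest on assumed prior durations and on how people recall, and should be read as an illustration. With a different follow-up stem, the remaining fault is unequal periods.

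The reach is small. This is one of 11 secondary outcomes, followed up only in the continue-oral-iron arm: 84/3 = 28 randomised, with 20 completers intended. No primary outcome or sample size uses it. It is still worth correcting, because Table 3 lists this scale among the outcomes whose collection the pilot is testing for a definitive trial.

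**What to change.** - Put one fixed recall period in the stem at both time points, for example the past 4 weeks, with the same four items.
- Append the follow-up form, so that its recall period can be seen.
- State in Section 2.2.2 that outcome 10 is the difference between these two fixed-period scores.
- Where feasible, use the same mode both times and keep the blinding arrangements: either self-completion returned only to the unblinded nurse, or administration by a nurse on both occasions, with the follow-up still done by the unblinded nurse.

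The cost is rewording a short, study-specific, non-validated form; no visit or contact is added. There are two downsides. The baseline form would no longer describe the whole oral iron history, which would need a separate question if it is wanted. A 4-week period at follow-up also leaves the earlier part of the trial period unasked, about 6 to 12 weeks given visits at 10 to 16 weeks. A somewhat longer fixed period would reduce that gap, provided that it does not exceed the 8 weeks of prior use guaranteed at entry.

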## **APPENDIX 3: CARE USE QUESTIONNAIRE**

RAINDroP: RAndomised IroN Deficiency anaemia management Pilot

#### **Care Use Questionnaire**

These questions help us to understand your use of health and social services because of your iron deficiency anaemia.

#### Iron deficiency anaemia

Some people with iron deficiency anaemia do not notice any problems or limitations. Other people notice problems, which may include:

- tiredness and lack of energy (lethargy)
- shortness of breath
- noticeable heartbeats (heart palpitations)
- a pale complexion.

More information is available from the study team, your doctor or the following website: https://www.nhsinform.scot/illnesses-and-conditions/nutritional/iron-deficiency-anaemia

Please read the questions carefully and write your answers in the spaces provided. If you cannot remember things exactly please give your best estimate. Feel free to add any of your own notes.

Version 1

Page 1 of 4 23/01/18

Participant ID:						

#### Hospital visits

1. a) Thinking back over the past three months, how many times have you been into hospital because of your anaemia?

	Number of visits	Reason for visit/s
For outpatient appointment		
For daycase appointment		
(for example: to see a doctor or to have a procedure carried out; no overnight stay)		
Overnight hospital stay		

b) If you had an overnight hospital stay, how many nights did you stay? Please tell us for each stay:

Stay 1 \_\_\_\_\_ Stay 2 \_\_\_\_\_ Stay 3 \_\_\_\_\_ Stay 4 \_\_\_\_\_

c) If you had a hospital visit or overnight stay, did you receive any of the following? (Please tick either yes or no)

	Yes	No
Iron "infusion" with a needle		
Iron tablets or medicine		
Blood transfusion		

Page 2 of 4

RAINDroP Care Use Questionnaire Version 1

30/01/18

Participant ID:						

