#### Table 4: Study Matrix

	Visit 1	Visit 2	Visit 3	Visit 4
	Combined	Randomisation	IV iron	3 month visit
	screening and	and telephone	administration visit	(1/2) weaks)
	baseline visit	call (+1 to 4 days)	(within 2 weeks of	(+/- 3 weeks)
			randomisation)	
Informed consent	X	X	X	Х
Inclusion/Exclusion Criteria	Х			
Demographics and medical	Х			
history				
Adverse Events Recorded		Х		Х
Height and weight	Х			
Medications	Х			Х
Oral Iron Use Scale	Х			X¶
Haemoglobin	Х			Х
Ferritin	Х			Х
C-reactive protein	Х			
Creatinine	X*			
eGFR	X*			
Short physical performance	Х			Х
battery				
Six-minute walk distance	Х			Х
Fatigue Severity Scale	Х			Х
Patient reported anaemia symptoms &	х			х
Quality of Life EQ-5D-5L & 15D	Х			Х
questionnaires				
Activities of Daily Living	Х			Х
(Nottingham EADL score)				
Health & Care Use	Х			Х
questionnaire				
Participants' experiences semi-				Х
qualitative questionnaire				
Randomisation (telephone call)		Х		
IV iron administration (if			Х	
required)				
Nutritional advice leaflet				Х

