#### 5.2 CONSENTING PARTICIPANTS

At the combined screening and baseline visit, written informed consent will be obtained by the local PI or delegate. The Delegation Log will detail staff (e.g. research nurses) who are appropriately qualified and trained staff and delegated to obtain informed consent. Where a participant requests to speak with a physician from the study team the consent process will not be completed until the participant has spoken to the physician and had all their questions answered to their satisfaction. Normal capacity is presumed (initial judgement is made by clinical team performing pre-screening; in addition, the RN will liaise with PI if any doubt or concern is raised when the PIS is provided / screening visit booked), where there is concern the PI or medically qualified delegate will assess capacity prior to any informed consent discussion; severe cognitive impairment (in the opinion of the investigator) is an exclusion criterion. Informed consent will cover all study procedures. A copy of the signed Informed Consent form will be retained at the study site and filed in the securely stored Investigator Site File (ISF) with an additional copy filed in the participant's medical notes.

Co-primary outcome data, including recruitment source will be provided via the PMS; this will be updated and Enrolment Log (filed within ISF) will be completed for all consented participants. Additional monthly Enrolment Log updates will be sent to the Trial Manager / delegate.

Eligibility and Informed Consent will be monitored as per the study Monitoring Plan

For participants recruited within NHS Fife specific written consent will be sought to link to routinely collected prescription, primary and secondary care use and social care data (see Section 0 and 0). This will be used to cross-validate information given by participants as preparatory work for using

such routinely collected data in a future large trial. The medication prescription data record linkage will be used as one of the measures to assess medication adherence.

A verbal consent check will be performed at each subsequent visit; recorded in participant medical record.

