#### 9.2 STATISTICAL ANALYSIS PLAN

All analyses will be by intention to treat, and will thus include all participants randomised. Data will be analysed by an independent statistician from Medical Statistics Team and a Research Assistant from HERU.

Baseline demographics and clinical characteristics will be presented as mean (SD), median (IQR) or percentage (n) as appropriate across study arms. Hb and ferritin level at 3 months will be compared across study arms using analysis of covariance with baseline Hb and ferritin level and site as covariates. Intra study arm comparisons will be assessed using the paired t-test or Wilcoxon signed rank test. Number of eligible patients per site, recruitment rate across sites, the proportions recruited by each method within site, dropout and crossover rates, all with corresponding 95% confidence intervals will each be tabulated. Effect size estimates of difference in Hb and ferritin level between arms will be calculated. The latest available SPSS version at the time of conducting statistical analysis will be used for analysis with intention to treat as the main analysis.

A per-protocol analysis will also be performed on completers of the study as a secondary analysis, primarily for safety outcomes (adverse event rates, falls).

Health economic measures (costs of healthcare use, comprising hospital stays for reasons related to

anaemia and outpatient/day case visits for iv iron administration, costs of blood transfusion and oral iron, and quality of life measurement using EQ-5D-5L and 15D) will be presented as unadjusted mean (SD) and median (IQR) values. Regression-based adjusted costs and quality of life values will also be calculated, with baseline cost, quality of life values, treatment group and patient demographics as co-variates. The percentage of missing data per resource use item and per quality of life questionnaire will also be presented.

We will assess both feasibility of secondary outcome measures and distribution of changes; these data will form the basis for sample size calculations for the full trial.

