## Community health services

2. Thinking back over the past three months, how many times have you seen or spoken to your GP because of your anaemia?

	Number of visits	Reason for visit/s
At the surgery?		
At home?		
Over the phone*?		
*Please only include calls made by you; not any received from your GP		

3. Thinking back **over the past three months**, how many times have you seen or spoken to a **nurse** from your local surgery **because of your anaemia**?

	Number of visits	Reason for visit/s
At the surgery?		
At home?		
Over the phone*?		
*Please only include calls made by you; not any received from the		
nurse		

÷									
	Participant ID:								
Ì									

4. Thinking back over the past three months, how many times have you used any other health or social care because of your anaemia?

	Number of visits	Reason for visit/s
A Home Help / Paid Care Worker?		
A Physiotherapist?		
An Occupational Therapist?		
A Speech Therapist?		
Other* ?;		
*Please state		

Page 4 of 4

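### The Visit 4 care-use form asks about an undated past three months, but the visit may fall three weeks either side of three months, so its counts can miss or add up to three weeks of care

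*Protocol*

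**What the plan says.** Appendix 3 opens its hospital section with "Thinking back over the past three months, how many times have you been into hospital because of your anaemia" and its community section with "Thinking back over the past three months, how many times have you seen or spoken to your GP because of your anaemia". The nurse and other-care questions use the same period. No item refers to randomisation or to the previous form, and the answer columns take only a number of visits and a reason.

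The form is completed twice. Table 4 marks it at the baseline visit and at Visit 4, and section 7.1.4 lists "Health & Care Use" among the Visit 4 questionnaires. The protocol prints one version, not labelled by visit.

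Table 4 places Visit 4 at three months with three weeks' tolerance either way, and the infusion "within 2 weeks of" randomisation. Randomisation and the telephone call follow the baseline visit by 1 to 4 days.

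Section 2.2.2 lists health care use among the outcomes whose collection is being tested. Section 9.2 costs it, naming "outpatient/day case visits for iv iron administration, costs of blood transfusion and oral iron" as components alongside anaemia-related hospital stays, and adjusts for baseline cost. In Fife, routine records will be linked; section 5.2 says of this: "This will be used to cross-validate information given by participants".

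**The concern.** The form looks back a fixed length from the day it is completed, whereas the period of interest runs from randomisation to Visit 4. The two coincide only when Visit 4 falls at exactly three months. If it falls later, the earliest post-randomisation contacts lie outside the question, and in the IV arm these may include the infusion visit, a cost component that section 9.2 names. If it falls earlier, contacts from before randomisation are counted as follow-up use. The same contact can then enter both the baseline-cost covariate and the outcome.

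Because the form takes no contact dates, its counts cannot be re-cut to the randomised period afterwards. An analysis plan could not fully repair this, so the wording has to be right when the data are collected.

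**Working it through.** **Inputs.** Recall length: three months, taken as 13 weeks (Appendix 3). Visit 4 at week v after randomisation, v from 13 − 3 = 10 to 13 + 3 = 16 (Table 4). Infusion at week u, from 0 to 2 (Table 4). Table 4 does not say which date the three months run from; randomisation is assumed.

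**Formulas.** Recall starts at week v − 13. Pre-randomisation weeks included = max(0, 13 − v). Post-randomisation weeks omitted = max(0, v − 13). The infusion is outside recall if u < v − 13.

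| v | Recall starts at week | Pre-randomisation weeks included | Post-randomisation weeks omitted | Infusions outside recall |
|---|---|---|---|---|
| 10 | −3 | 3 | 0 | none |
| 11 | −2 | 2 | 0 | none |
| 12 | −1 | 1 | 0 | none |
| 13 | 0 | 0 | 0 | none |
| 14 | 1 | 0 | 1 | those before week 1 |
| 15 | 2 | 0 | 2 | those before week 2 |
| 16 | 3 | 0 | 3 | all |

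**Extremes.** At week 10, 3/13 = 23% of the recalled time precedes randomisation. At week 16, 3/16 = 19% of follow-up is not asked about.

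**Overlap with the baseline form.** A week-10 form reaches back 21 days before randomisation. The baseline form was completed 1 to 4 days before randomisation, so it has already covered 17 to 20 of those 21 days.

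**Sensitivity to the definitions.** Taking three months as 12 weeks moves every row one week earlier and leaves the offsets unchanged. If Visit 4 is timed from the baseline visit, v falls by 1 to 4 days. The most that can be included becomes 3 weeks and 4 days, and the most omitted 2 weeks and 6 days.

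**Illustration only.** The documents give no distribution of visit dates. Assume infusions uniform over weeks 0 to 2 and recall that stops exactly at 13 weeks.

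- Visit 4 uniform over weeks 10 to 16: the probability that the infusion is outside is E[(3 − u)/6] = (3 − 1)/6 = 1/3.
- Visit 4 normal around week 13: about 15% with SD 0.75 week, 19% with SD 1 and 26% with SD 1.5.
- Mean pre-randomisation time included: 0.75 week (0.75/13 = 5.8% of recall) if uniform, and 0.40 week (3.1%) if normal with SD 1.

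**With a form dated from randomisation.** Pre-randomisation weeks included and post-randomisation weeks omitted are both 0 at every v from 10 to 16, and no infusion falls outside. Observed time then varies from 10 to 16 weeks.

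**The case against.** **A fixed three-month recall at a three-month visit is ordinary.** It also keeps the follow-up period equal in length to the baseline period, which is useful when baseline cost is a covariate. This stands as a cost of the change, but it does not remove the mismatch at visits away from week 13.

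**The infusion has a second source.** Under section 8.1 the unblinded research nurse records iron treatment separately, and those data go to the health economics unit. Appendix 3 also asks whether an iron infusion was received and why each visit took place, so a reported infusion can be reconciled with that record. Section 12.3 refers to a health economic analysis plan, not shown here, which may choose the source. Most of this stands. A reader might infer that infusion costs will be lost, or counted twice if the record is added to the form; the documents establish neither. They only leave the costing source unstated.

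**Other contacts have partial back-up.** Section 7.2 provides for direct questioning on care contacts and a hospital record review at Visit 4, and the components listed in section 9.2 do not include GP, nurse or therapist contacts. This lessens the effect on costs. But it is safety collection, not a resource log, and health care use is an outcome in its own right.

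**The Fife comparison.** A reader might infer that cross-validation will score the window mismatch as a reporting error. That does not follow. Routine records that carry dates can be cut to whatever period the form asked about, and no section fixes a different one.

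**Memory does not stop at 13 weeks.** The form invites best estimates, and an infusion is memorable. This stands, so the figures describe the question as worded and do not predict what participants will report.

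**Conclusion.** The point holds in a limited form. As worded, the Visit 4 form can omit up to 3 post-randomisation weeks when the visit is late and include up to 3 pre-randomisation weeks when it is early. An on-schedule infusion is outside the question from about week 15 and may or may not be between weeks 13 and 15. Pre-randomisation care can enter in any arm; omission of the infusion concerns the IV arm only.

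This rests on three months being about 13 weeks, on Visit 4 being timed from randomisation, and on the printed form being the one used at Visit 4.

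Two stronger readings are not supported. One is that every late visit drops the infusion: at week 14 only infusions before week 1 are outside. The other is that some fifth to a third of the IV arm will lose its infusion cost: those fractions come from assumed visit dates and an exact memory cut-off, and the iron treatment record probably recovers the infusion.

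The co-primary recruitment outcomes are untouched. The consequence is modest and confined to the secondary health care use and cost outcome, but the correction is cheap and has to be made before the data are collected.

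**What to change.** On the Visit 4 version only, replace *over the past three months* with *since [date of randomisation]*, with the date filled in by the site. The date does not reveal the arm, so assessor blinding is kept. Leave the baseline version as it is.

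State in the analysis that the infusion contact is counted once, from the iron treatment record, and is not converted to a rate. It occurs early, so dividing by follow-up time would give 1/10 per week at a week-10 visit and 1/16 at week 16, a 1.6-fold difference for the same event. For the other contacts, account for actual follow-up length, for example by scaling to 13 weeks (a factor of 13/v) or by including follow-up time in the model. Cut the Fife linked records to the same dates as the form.

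The cost is a new version of one appendix and a short addition to the analysis, with no extra visits or staff. The drawbacks are recall up to three weeks longer at late visits, and a follow-up period that varies and no longer equals the baseline recall period.
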